## **Study protocol**

**Official title: Welfare benefits for individuals with functional somatic disorders**

***DanFunD***

### **Background**

Functional somatic disorders (FSD) are common conditions characterized by persistent patterns of physical symptoms that cannot be better explained by other physical or mental conditions (1). The conditions may cause severe impairment for the patients who present with reduced physical and mental health, lower social status, and poor labour market association (2-4).

In 2005, it was estimated that FSD accounted for 3% of hospitalizations and 10-20% of health care expenses in Denmark (5), and a newer Danish primary care study has shown patients with FSD to have higher annual health care costs compared with conventionally-defined conditions (6). In other countries, studies in clinical samples have shown increased direct and indirect health care costs of FSD (7, 8) showing a dose-response relationship with severity of the FSD (9). These studies into highly selected clinical samples may induce high risk of selection bias, and studies including random selected general population samples are therefore needed. One Canadian population-based study on health care costs of children, adolescents, and young adults with FSD also found increased health care use and costs for this group (10). Studies investigating the socioeconomic burden in terms of welfare benefits of FSD in an adult random sample from the general population are, however, lacking.

### **Objective**

To estimate the number of weeks of welfare benefits, i.e. sickness benefit, unemployment benefit and social assistance, for individuals with FSD and compare them to individuals without FSD and individuals with severe physical disease.

### **Data**

Data from the DanFunD baseline cohort will be included (11); individuals with FSD are identified by means of self-reported questionnaires (n=9,656) (2) and diagnostic research interviews (n=1,590) (12). Individuals with severe physical disease are identified by self-reported questionnaires.

---

 Given the circumstances that interview-data are uploaded in Statistics Denmark

*Dependent variable:*

Data on welfare benefits will be obtained from The Danish Register for Evaluation of Marginalization (DREAM) which contains data on Danish citizens who have received social benefits or other welfare payments (13). Welfare benefit will be counted as number of weeks per year in a 10-year period before and 5-year period after the day the participant participated in the DanFunD baseline investigation.

Welfare benefits will be grouped into 7 categories where categories 1-3 are the main categories for investigation and categories 4-7 are used in order to exclude weeks of no transfer income/self-support, public retirement pension, emigration, and death (Table 1).

**TABLE 1**

Category	Explanation	Coding in DREAM (Danish)
1) Sickness benefit	Individuals who receive sickness benefits such as employed citizens being ill, unemployed citizens currently ill, citizens in activation programs currently ill, and citizens in flexible jobs but currently ill	Ledighedsydelse (740, 743-748) Revalidering (760, 763-768) Fleksjob (771) Fleksjob, Sygedagpenge under fleksjob (774) Ressourceforløb (810, 813-818) Jobafklaring (870, 873-878) Sygedagpenge (890, 893-899)
2) Unemployment benefits	Unemployed citizens who receive unemployment benefit (full or part time, during vacation or activation) together with citizens on social assistance who are deemed ready-to-work, only receiving social assistance because of unemployment, but having no entitlement to unemployment benefit.	Dagpenge, ledighed (111) Supplerende dagpenge, ledighed (115) Kontanthjælp, jobparate (130, 133-139) Uddannelseshjælp, åbenlyst uddannelsesparat (140, 143-149) Uddannelseshjælp (720, 723-729) Kontanthjælp (730, 733-739)
3) Social assistance	A welfare payment administered by the municipal social service department and is allocated if citizens are unable to support themselves.	Skånejob (781) Førtidspension (783)
4) No transfer income/self-support	Individuals that do not receive welfare payments under the circumstances of sickness, unemployment, or social benefits. Including leave-of-absence schemes and grants from State Education Fund.	Voksenlærlinge (521) Efterløn (621) SU med ydelse (651) SU uden ydelse (652) Voksen uddannelsesstøtte og staten voksen uddannelsesstøtte (661) Barseldagpenge (881)

5) Public retirement pension	Folkepension (998)
6) Emigration	Ikke bosiddende i Danmark (997)
7) Death	Død (999)

*Independent variables:*

Participants with FSD will be defined as follows:

- FSD operationalised by the Bodily Distress Syndrome single- and multi-organ type will be defined with both self-reported questionnaires (14) and diagnostic interviews (3)
- Three functional somatic syndromes, i.e. irritable bowel (15), chronic widespread pain (16), and chronic fatigue (17) will be defined with questionnaires

Severe physical disease will be defined as having received at least one of the following five diagnoses: Cancer, stroke, myocardial infarction, other heart disease, and obstructive pulmonary disease.

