**Analytical plan**

Analyses will be conducted by Stata Statistical Software, version 17 (18). Separate analyses for each time period (10 years before and 3 years after the DanFunD baseline investigation) will be conducted.

*FSD case/FSD non-case descriptives:*

Percentages of participants having received at least one week of welfare benefits during the 10-year period before baseline and the 5-year period after baseline will be calculated for each FSD definition and displayed in figures (see example in Figure 1).

 Given the circumstances that interview-data are uploaded in Statistics Denmark

[figure not shown]

Figure 1

*FSD case/FSD non-case differences:*

To compare the mean number of weeks receiving sickness benefit, unemployment benefit, and social assistance, respectively, between cases and non-cases of FSD, linear regression analyses on each of the three main welfare variables will be performed with welfare benefit variables as the continuous dependent variable and the dichotomous FSD case-status variables as the primary independent variable.  $\beta$ -coefficients with 95% confidence intervals (CI) will be used as measure of association, and all analyses will be adjusted for sex and age. Linearity of age will be checked by expanding the model with natural cubic splines with five knots at the 5th, 27.5th, 50th, 72.5th, and 95th percentiles according to the recommendations by Harrell (19). Deviations from linearity will be tested using a  $\chi^2$ -test ( $p < 0.05$ ). To account for the possible positive skew and outliers in the welfare variables, optimally non-parametric bootstrap resampling with 100,000 repetitions will be performed. Significance will be judged from 95% bootstrapped CI of differences not overlapping with 0. If the assumptions for performing non-parametric bootstrap resampling are not fulfilled, generalized linear models will be used instead.

To compare the odds of having received at least one week of sickness benefit, unemployment benefit, or social assistance, between cases and non-cases of FSD, logistic regression analyses will be performed with welfare benefit variables as the dichotomous dependent variable and the dichotomous FSD case-status variables as the primary independent variable. Odds ratio with 95% CI will be used as measure of association.

*FSD case/severe physical disease descriptives:*

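### Table 1's definitions and code lists conflict for the main outcomes: code 771 in sickness benefit, the 720s and 730s in unemployment benefit, and the name of category 3

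*SAP*

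**What the plan says.** The SAP's Objective is to estimate weeks of welfare benefits, "i.e. sickness benefit, unemployment benefit and social assistance". The Data section states that "categories 1-3 are the main categories for investigation", and Table 1 gives each category a name, an explanation and a list of DREAM codes.

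- **Category 1, sickness benefit.** The explanation covers people who receive sickness benefits and gives examples. The one on flexible jobs is "citizens in flexible jobs but currently ill". The code list contains "Fleksjob (771) Fleksjob, Sygedagpenge under fleksjob (774".
- **Category 2, unemployment benefits.** Besides recipients of unemployment benefit, the explanation admits "citizens on social assistance who are deemed ready-to-work, only receiving social assistance because of unemployment". The code list has the 130s (labelled job-ready) and the 140s (labelled clearly education-ready), and also "Uddannelseshjælp (720, 723-729) Kontanthjælp (730, 733-739", with no such label.
- **Category 3, social assistance.** The explanation speaks of a municipal payment to citizens who cannot support themselves. The complete code list is "Skånejob (781) Førtidspension (783".

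The Analytical plan calls for "Separate analyses for each time period". It fits a linear regression of weeks on FSD status for each of the three categories, and logistic regressions for having received at least one week.

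**The concern.** The code list decides which weeks enter an outcome. The name and explanation decide how the result is read. In Table 1 they cannot both be followed.

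If the code list is followed, the sickness-benefit difference between FSD cases and non-cases includes flexible-job weeks with no stated illness. A single such week makes a participant positive in the model for at least one week of sickness benefit. The unemployment outcome may likewise include cash-assistance weeks of people who were not ready to work, whom its own text leaves out. A result reported for social assistance would describe disability pension and sheltered jobs. If this stays open until the data are seen, the content of a main outcome can be settled after the results are known.

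**Working it through.** The SAP states no benefit frequencies, so there is no figure to reproduce. The check compares text with codes and then counts the models that could change.

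**Category 1 codes (Table 1).** 740s 7 + 760s 7 + 771 1 + 774 1 + 810s 7 + 870s 7 + 890s 8 = 38.
- Labels that state sickness benefit (Sygedagpenge): 774 and the 890s, 1 + 8 = 9.
- Labels that do not: 38 − 9 = 29, namely 771 and 28 others (740s, 760s, 810s, 870s).
- 771 is the clearest conflict, because the text sets an explicit illness condition for flexible jobs and the code that meets it (774) is listed separately.

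**Category 2, cash and education assistance.** 130s 8 + 140s 8 + 720s 8 + 730s 8 = 32. With a readiness label: 8 + 8 = 16. Without: 8 + 8 = 16.

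**Category 3.** Two codes, 781 and 783. None is cash or education assistance, although the category 2 text applies the term social assistance to recipients who are coded in category 2.

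**Models that could change.** Three outcomes × two periods = 6 linear models per FSD definition. The count of FSD definitions in the SAP runs from 4 (three syndromes plus Bodily Distress Syndrome by questionnaire) to 7 (three syndromes plus single- and multi-organ type, each by questionnaire and by interview).

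| Change | Linear models per definition | 4 definitions | 7 definitions |
|---|---|---|---|
| Take 771 out of the three main categories | 1 × 2 = 2 of 6 | 8 of 24 | 14 of 42 |
| Move the 720s/730s from category 2 to category 3 | 2 × 2 = 4 of 6 | 16 of 24 | 28 of 42 |
| Rename category 3 | 0 of 6 | 0 | 0 |

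If 771 weeks are placed in category 2 or 3, that category's models change as well. The matching logistic models follow the same pattern if they are fitted per category. In the comparison with severe physical disease, if the three categories are merged, moves between them cancel, but removing 771 weeks from all three does not.

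**Illustration under assumed shares.** Suppose the share of people in 771 for the whole window, and never ill, is higher in cases than in non-cases by d. The difference in mean weeks then shifts by d × 52 × years. For d = 0.5 to 5 percentage points this is 0.005 × 520 = 2.6 to 0.05 × 520 = 26.0 weeks over 10 years, and 1.3 to 13.0 weeks over 5 years (260 weeks).

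For at least one week, let p be the share with true sickness benefit, equal in both groups, and f the share of the remainder with 771 weeks only. The positive share is p + (1 − p)f. With p = 20 to 40%, f = 1% in non-cases and 2 to 5% in cases, the odds ratio is 1.025 to 1.202 instead of 1.00. For example, p = 20% and f = 5% against 1% give 0.240 against 0.208, and (0.240/0.760)/(0.208/0.792) = 1.202. None of these shares comes from the SAP.

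**The case against.** The strongest reply is that the category 1 explanation only gives examples, so the group may have been meant as a broad health-related one, loosely described. On that view 771 is no odder than the 28 other codes whose labels do not mention sickness. Part of this stands: the mismatch is wider than 771, and removing 771 alone would not make category 1 a pure sickness-benefit outcome. But the open list does not resolve the conflict. The explanation still requires receipt of sickness benefits, its only wording on flexible jobs requires current illness, and the SAP never says that 771 marks reduced work capacity.

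It can also be said that category 3 is a matter of naming, since Table 1 shows its codes openly and its explanation can fit them. This stands: a new name moves no weeks.

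A reader might infer that all 32 cash- and education-assistance codes belong in category 3. The SAP does not support that. The category 2 text deliberately counts ready-to-work recipients as unemployed, and the 16 codes in the 130s and 140s are labelled accordingly. Only the 720s and 730s are unexplained, and they may yet prove to fit.

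**Conclusion.** The point holds as a conflict between definitions and codes in main outcomes. Code 771 contradicts the category 1 text. The 720s and 730s are not shown to meet the category 2 text. The name of category 3 does not match its content.

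Taking 771 out can change 2 of 6 linear models per FSD definition, and keeping it under a corrected name changes none. The effect of the 720s and 730s depends on whether they are reassigned, and where.

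A reader might conclude that the category 1 and category 3 results are both numerically wrong, 4 of 6 models per definition. That goes too far, because the category 3 fault changes the interpretation and no coefficient. Nor can it be said that the FSD estimates are biased by a known amount or in a known direction. The SAP gives neither the frequency of these weeks nor their distribution between cases and non-cases. The counts rest on two analysis periods and 4 to 7 FSD definitions.

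**What to change.** Before analysis:

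1. **Category 1.** Either take 771 out, keep 774 and state which category receives 771 weeks; or keep 771, drop the illness condition for flexible jobs and rename the outcome as a broader health-related benefit. The second option also fits the 740s, 760s, 810s and 870s. If the first is chosen, the text still has to be squared with those 28 codes.
2. **Category 2.** Confirm that the 720s and 730s meet the ready-to-work condition. If not, reassign them or reword the explanation to cover all cash and education assistance.
3. **Category 3.** Rename it to match its two codes (disability pension and sheltered job), in Table 1 and in the four other places that use the name: once in the Objective, twice under FSD case/FSD non-case differences, and once under FSD case/severe physical disease differences. If category 1 is renamed, change its name in the same four places.

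The cost is a few edits to codes, sentences and outcome names. The register extract stays the same, and no new data or added analysis is needed.

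### Category 2 (unemployment benefits) in Table 1 is defined for ready-to-work assistance recipients, but 16 of its 34 codes carry no readiness label

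*SAP*

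**What the plan says.** Table 1 gives each benefit category an explanation and a list of DREAM codes.

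**Category 2, explanation.** Besides people on unemployment benefit, it admits assistance recipients on a condition: "together with citizens on social assistance who are deemed ready-to-work, only receiving social assistance because of unemployment", "but having no entitlement to unemployment benefit".

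**Category 2, codes.**
- Unemployment benefit proper: "Dagpenge, ledighed (111) Supplerende dagpenge, ledighed (115"
- Cash assistance labelled ready for work: "Kontanthjælp, jobparate (130, 133-139"
- Education assistance labelled obviously ready for education: "Uddannelseshjælp, åbenlyst uddannelsesparat (140, 143-149"
- The same two benefits with no label: "Uddannelseshjælp (720, 723-729) Kontanthjælp (730, 733-739"

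**Category 3 (social assistance).** It is explained as "A welfare payment administered by the municipal social service department and is allocated if citizens are unable to support themselves", and its codes are only "Skånejob (781) Førtidspension (783".

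The Data section names categories 1-3 as the main ones. The Analytical plan, under FSD case/FSD non-case differences, models each of the three separately: linear regression for the number of weeks and logistic regression for at least one week.

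**The concern.** The explanation sets a readiness condition, and the table's own labels show that DREAM has codes carrying it. If the explanation governed, the labelled series would be enough. With the plain series listed as well, every cash- and education-assistance code in Table 1 goes to category 2, and the condition removes no code.

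At stake is what one of three main outcomes means. A reader of the results would be told that category 2 measures unemployment among people able to take work, while its codes do not confine it to them. Because unemployment and social assistance are separate outcomes, the place given to these weeks affects how a case/non-case difference in either one is read. Adjustment for age and sex, or bootstrapping, does not change which weeks an outcome contains.

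**Working it through.** The SAP states no figure on this point, so there is none to reproduce. The check is a count of codes and a search for any restriction elsewhere.

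**Step 1. Count the category 2 codes.** The input is the Table 1 code column, with each range read as consecutive integers. A series such as 130, 133-139 has 1 + 7 = 8 codes.

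| Line in category 2 | Codes | Readiness label |
|---|---|---|
| 111 and 115 | 2 | not applicable (unemployment benefit) |
| 130, 133-139 | 8 | ready for work |
| 140, 143-149 | 8 | obviously ready for education |
| 720, 723-729 | 8 | none |
| 730, 733-739 | 8 | none |
| **Total** | **34** | |

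- Codes without a label: 8 + 8 = 16.
- Share of all category 2 codes: 16/34 = 47%.
- Share of the assistance codes: 16/32 = 50%.
- Codes left if the plain series were taken out: 34 − 16 = 18.

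The 140 series is labelled for education, not work. If it too were held to the literal wording, the codes outside the definition would be 16 + 8 = 24 of 34 (71%). The count of 16 is the more lenient reading.

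All of these are shares of codes, not of weeks.

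**Step 2. Look for a restriction or another home for these codes.** Categories 1, 3 and 4 list no cash- or education-assistance code. Neither the Data section nor the Analytical plan limits the plain series to ready-to-work recipients or to particular years.

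**Step 3. Follow the codes into the models.** Assume each week carries one code. A person's category 2 weeks are then

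weeks(category 2) = weeks(111, 115, 130s, 140s) + weeks(720s, 730s).

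Linear regression with the same covariates is additive in the outcome, so

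β(category 2) = β(without plain series) + β(plain series).

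The reported coefficient differs from the one for the labelled codes by exactly β(plain series). The SAP gives no week counts by code, so neither the size nor the sign of that term can be worked out. For the outcome of at least one week, adding codes can only leave the percentage in each group unchanged or raise it. The effect on the odds ratio is not determined.

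**The case against.** The strongest reply is that Table 1 gives short Danish labels and defines no code. The plain series could hold only people not ready for work, a mix, or every recipient from years before a readiness split existed. The last is plausible with a 10-year look-back. The code list is explicit and reproducible, so the smallest repair may be to the explanation. This stands. It means that inclusion of people not ready for work is possible, not shown, and that moving all plain codes by default could put ready-to-work weeks in the wrong category. It does not remove the mismatch, since under each of these readings the stated condition is either broken or cannot be verified for those weeks.

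A reader might go further and infer that FSD cases too unwell to work are being scored as unemployed, so that a higher FSD coefficient for unemployment would be spurious. The document does not support that:

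- Nothing in it says that being on the 720 or 730 series is health-related, and lacking a readiness label is not the same as incapacity.
- Several illness-related states are already coded elsewhere. Category 1 takes unemployed people and people in activation programmes while ill, and category 3 takes code 783 (Førtidspension).
- The weeks in question are real benefit weeks whose category is unsettled, and no case/non-case difference in them is given.

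The Background does describe poor labour market association in FSD, so a difference in these weeks is conceivable, but it would be an assumption.

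**Conclusion.** The explanation and the code list of category 2 do not match, and nothing else in the SAP reconciles them. As coded, the unemployment outcome is not limited to the population stated for it: 16 of 34 codes (47%) carry no readiness label, and the outcome may include assistance weeks of people not assessed as ready for work.

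The conclusion rests on the table's own labels and on reading the code ranges as consecutive integers. It does not depend on what category 3 is called. It does not establish bias in the FSD comparison, because the weeks affected and their distribution between cases and non-cases cannot be sized from the document. A main outcome that departs from its own definition should be settled before the data are analysed.

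**What to change.** Before analysis, check the content of the 720, 723-729 and 730, 733-739 codes against the DREAM code book, by calendar period. Then:

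1. **Where the plain codes denote people not assessed as ready to work,** take them out of category 2 into a separately reported category, or into category 3 if its definition fits.
2. **Where they are mixed or predate the readiness split,** keep them in category 2, widen its explanation to say so, and report the category 2 results with and without the 720 and 730 series.
3. **In either case,** word the explanation so that it also covers the education-assistance series, whose label concerns education rather than work. If a new category is created, say whether its weeks enter the median-split comparison with severe physical disease.

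The cost is a code-book check, a change to Table 1 and its recode, and one sensitivity analysis, with no new data. If codes are moved, category 2 may hold fewer weeks, and its series may show a break over calendar time. That break should be described alongside the 10-year results.

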**Analytical plan**

Analyses will be conducted by Stata Statistical Software, version 17 (18). Separate analyses for each time period (10 years before and 3 years after the DanFunD baseline investigation) will be conducted.

*FSD case/FSD non-case descriptives:*

Percentages of participants having received at least one week of welfare benefits during the 10-year period before baseline and the 5-year period after baseline will be calculated for each FSD definition and displayed in figures (see example in Figure 1).

 Given the circumstances that interview-data are uploaded in Statistics Denmark

[figure not shown]

Figure 1

*FSD case/FSD non-case differences:*

To compare the mean number of weeks receiving sickness benefit, unemployment benefit, and social assistance, respectively, between cases and non-cases of FSD, linear regression analyses on each of the three main welfare variables will be performed with welfare benefit variables as the continuous dependent variable and the dichotomous FSD case-status variables as the primary independent variable.  $\beta$ -coefficients with 95% confidence intervals (CI) will be used as measure of association, and all analyses will be adjusted for sex and age. Linearity of age will be checked by expanding the model with natural cubic splines with five knots at the 5th, 27.5th, 50th, 72.5th, and 95th percentiles according to the recommendations by Harrell (19). Deviations from linearity will be tested using a  $\chi^2$ -test ( $p < 0.05$ ). To account for the possible positive skew and outliers in the welfare variables, optimally non-parametric bootstrap resampling with 100,000 repetitions will be performed. Significance will be judged from 95% bootstrapped CI of differences not overlapping with 0. If the assumptions for performing non-parametric bootstrap resampling are not fulfilled, generalized linear models will be used instead.

To compare the odds of having received at least one week of sickness benefit, unemployment benefit, or social assistance, between cases and non-cases of FSD, logistic regression analyses will be performed with welfare benefit variables as the dichotomous dependent variable and the dichotomous FSD case-status variables as the primary independent variable. Odds ratio with 95% CI will be used as measure of association.

*FSD case/severe physical disease descriptives:*

Percentages of participants receiving at least one week of welfare benefits during the 10-year period before baseline and the 5-year period after baseline will be calculated for individuals with FSD (and no severe physical disease) and individuals with severe physical disease (and no FSD) and displayed in figures (see example in Figure 1).

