#### *FSD case/severe physical disease differences:*

To compare the odds of having received sickness benefit, unemployment benefit, or social assistance, between FSD cases and individuals with severe physical disease, logistic regression analyses will be performed with welfare benefit variables merged into a dichotomous dependent variable with two levels (0 = number of weeks < the median number in the total sample (reference), 1 = number of weeks  $\geq$  the median value in the total sample) and a dichotomous primary independent variable with two levels (0 = severe physical disease (reference) and 1 = FSD). Odds ratio with 95% CI will be used as measure of association.

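### The post-baseline window is 3 years in the sentence that sets the analysis periods but 5 years in the outcome definition and both descriptive paragraphs, and no regression paragraph names a window

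*SAP*

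**What the plan says.** The SAP gives the length of the post-baseline period in four places.

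- **Data, dependent variable:** "Welfare benefit will be counted as number of weeks per year in a 10-year period before and 5-year period after the day" of the baseline investigation. This is 5 years.
- **Analytical plan, opening paragraph:** "Separate analyses for each time period (10 years before and 3 years after the DanFunD baseline investigation) will be conducted". This is 3 years.
- **FSD case/FSD non-case descriptives:** the percentages with any benefit are those "during the 10-year period before baseline and the 5-year period after baseline will be calculated for each FSD definition". This is 5 years.
- **FSD case/severe physical disease descriptives:** again "the 10-year period before baseline and the 5-year period after baseline will be calculated for individuals with FSD". This is 5 years.

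Three inferential analyses follow, and none states a period:

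- the linear regression, whose aim is "To compare the mean number of weeks receiving sickness benefit, unemployment benefit, and social assistance, respectively";
- the logistic regression on "the odds of having received at least one week of sickness benefit, unemployment benefit, or social assistance";
- the comparison with severe physical disease, which uses "welfare benefit variables merged into a dichotomous dependent variable with two levels", split at the total-sample median.

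**The concern.** The follow-up window is part of the outcome in every post-baseline model. The regression paragraphs must take it from elsewhere in the SAP, and the two possible sources disagree. The Data section defines the outcome over 5 years. The only sentence that assigns periods to the separate analyses says 3.

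Two things are at stake. First, the choice stays open until the data are in hand, when it could be made with results in view. Second, models and figures could cover different periods. The clearest case is the outcome of at least one week of benefit: its percentages are explicitly over 5 years, while the odds ratios for the same outcome could be over 3. A reader would then set an odds ratio beside percentages that do not belong to it.

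This reaches all three benefit categories, every FSD definition and both comparisons (with non-cases and with severe physical disease) on the post-baseline side.

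**Working it through.** The SAP gives no sample size, power or event count that depends on the window, so there is no figure of its own to reproduce. The check sets the texts side by side and then asks how far the two lengths can differ.

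**1. Texts side by side**

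| Place in the SAP | Before baseline | After baseline |
|---|---|---|
| Data, dependent variable | 10 years | 5 years |
| Analytical plan, opening paragraph | 10 years | **3 years** |
| FSD case/non-case descriptives | 10 years | 5 years |
| FSD/severe physical disease descriptives | 10 years | 5 years |
| Linear regression on mean weeks | not stated | not stated |
| Logistic regression, at least one week | not stated | not stated |
| Logistic regression, median split | not stated | not stated |

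The pre-baseline window agrees in all four places that give one. The post-baseline window is 5 years three times and 3 years once. Nothing says that the models use a shorter window than the descriptives, or gives a reason for one.

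**2. Mean weeks**

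The result depends on whether weeks are summed over the window or expressed per year. The Data section counts weeks per year; the regression paragraph speaks only of the mean number of weeks.

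- Summed, at 52 weeks a year: 3 × 52 = 156 and 5 × 52 = 260. With a constant yearly difference *d* between cases and non-cases, the summed differences are 3*d* and 5*d*. The 3-year value is smaller by 1 − 156/260 = 0.40, or 40%.
- Per year: 3*d*/3 = 5*d*/5 = *d*, a change of 0%.

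At a constant rate the range is therefore 0% to 40%.

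**3. At least one week of benefit**

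The SAP gives no yearly probability of receiving benefit, so *p* is an assumption. With independent years, the proportion with any benefit over *n* years is 1 − (1 − *p*)^*n*.

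| Assumed yearly *p* | 3 years | 5 years |
|---|---|---|
| 5% | 1 − 0.95³ = 14.3% | 1 − 0.95⁵ = 22.6% |
| 10% | 1 − 0.90³ = 27.1% | 1 − 0.90⁵ = 41.0% |
| 20% | 1 − 0.80³ = 48.8% | 1 − 0.80⁵ = 67.2% |

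If the same people receive benefit every year, both windows give *p* and the gap vanishes. The table is therefore an upper illustration. Counting weeks per year does not remove this effect, because the outcome is whether any week occurred in the window.

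**4. Median split**

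If weeks are summed, the total-sample median can differ between windows, and people can change group. The SAP gives no distribution of weeks, so the shift cannot be sized. If more than half the sample has no benefit weeks in either window, the median is 0 in both and the cut-off does not move.

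**The case against.** The best defence is that this is one stray number. The models use the welfare benefit variables, and the Data section defines how these are counted: over 5 years after baseline. On that reading the regressions inherit 5 years and need not repeat it. The 3-year sentence also stands above the whole Analytical plan, descriptives included, and the descriptive paragraph beneath it says 5. If the sentence truly governed, it would be contradicted at once. A 3-year model beside a 5-year figure arises only if the sentence is applied to the models alone, which no text says.

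The sizes can be challenged too. The 40% needs summed weeks, whereas the only stated unit is weeks per year. The proportions rest on assumed probabilities and independent years. They also describe percentages, which the descriptive paragraphs already fix at 5 years, and not the odds ratios that are in doubt.

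Much of this is fair. A drafting slip is the likeliest origin, 5 years is the likelier intent, and the silence of the regression paragraphs is not a further contradiction. The limits on the figures also stand. But inheritance from the Data section is plausible and not forced: the conflicting number sits in the one sentence that assigns periods to the analyses, and an analyst who followed it literally would be following the plan. Nothing in the SAP says which statement prevails.

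**Conclusion.** The contradiction is real, and the SAP does not resolve it. The period for the post-baseline regressions is not fixed; the pre-baseline analyses are unaffected.

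At a constant benefit rate, the effect on mean differences lies between none (weeks per year) and a 40% reduction with 3 years (summed weeks). For any benefit, the gap between windows runs from zero under full persistence to 8.3, 13.9 and 18.4 percentage points (22.6 − 14.3, 41.0 − 27.1 and 67.2 − 48.8) for assumed yearly probabilities of 5%, 10% and 20% with independent years. No size or direction can be given for the odds ratios.

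The case for correction does not rest on these illustrations. Every post-baseline model needs one window, and the plan offers two. It must be settled before analysis.

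**What to change.** In the opening paragraph of the Analytical plan, change the post-baseline period from 3 to 5 years, in line with the Data section and both descriptive paragraphs. Add one clause stating that this window applies to all post-baseline descriptives and to the linear, logistic and median-split regressions. If 3 years is what the sponsor intends, change the other three places instead and add the same clause.

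The cost is one number and one clause (three numbers and one clause if 3 years is kept).
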